meta-analyses. With a final expected sample size of 215 (86, 86, 54 in Tele-Savvy (TS), attention control (AC), and usual care (UC) groups respectively), for the primary intervention test (group-by-time effect) comparing the outcomes of the three group changes from T1 to T2 to T3 (3-by-3 repeated measures design of three groups measured at three time points), at 80% power and 5% significance level, small-to-moderate effect sizes, Cohen's $f = 0.21-0.24$ may be detected for the main effects for group, time and group-by-time interaction effects (given moderate correlation between measurement pairs of $r=0.3-0.5$) (power analysis using PASS 14 Power Analysis and Sample Size Software (2015). NCSS, LLC. Kaysville, Utah, USA, ncss.com/software/pass). After adjusting for any potential group differences, the overall intervention effect of the Tele-Savvy program for the combined T1-to-T3 pre-post effects for the immediate Tele-Savvy group plus the T3-to-T5 pre-post effects from the AC and UC groups will yield a total estimated 215 subjects to perform a pre-post test to detect a small effect size of $d=0.19$ at 80% power and 5% significance level. With the pooled sample, we will be able to also test the mediating effects of mastery and self-efficacy on the Tele-Savvy program for the caregiver outcomes. As shown by Fritz and MacKinnon (2007), sample sizes of 148-196 were adequate to achieve 80% power to detect small-to-moderate effect sizes for the indirect effect of the independent variable on the dependent variable through the mediating variable considering both the Sobel test as well as percentile and bias-corrected bootstrapped approaches.¹⁰⁸ Although our analytic strategy is robust to missing data we will enroll 270 CGs (108 for TS and AC groups and 54 for UC group) per consideration 1 above (maximize accommodation) allowing for an expected 20% attrition. For the exploratory aim comparing the program's efficacy across the 3 ethnicity groups, with an expected final sample size of 215 subjects and proportions of approximately 65% Caucasian, 20% African American, 15% Hispanic, at 80% and 5% level of significance, we will be able to detect moderate effect sizes Cohen's $f=0.19-0.23$ (for 3-group by 2-time point RM-ANOVA for group, time and group-by-time effects).

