Aims 1, 2 and 3 (a). Our primary aims are concerned with assessing the effect of the Tele-Savvy program for reducing or retarding the burden, depression, and anxiety of Alzheimer's family caregiving, promoting the quality of life of persons with Alzheimer's (BPSD, agitation; Quality of Life; affect), and enhancing caregiver mastery. We will employ multi-level mixed effects models (MLM) with random (participant) and fixed (cohort) effects to test linear (and non-linear) trajectories of change for the intervention groups and model group X time and group*time interactions. To compare the Tele-Savvy intervention to the attention control and usual care groups, the first 3 time points will be used to test for differences between the 3 group longitudinal trajectories. Additionally, we will combine the intervention effects for the three groups across the main 3 time points from just before receipt of the intervention to immediately after the intervention to the 1st follow-up time point (T1-to-T2-to-T3 for the immediate group and T3-to-T4-to-T5 for the attention control and usual care groups respectively). These combined time points will be referred to as cT1, cT2, cT3. If there are significant differences between or among the 3 groups at the time point immediately prior to receipt of the intervention (cT1), these "baseline" effects will be included and adjusted for in the final model. Overall time effects will be assessed as well as planned post hoc comparisons for immediate effects (cT1 to cT2), longer term effect (cT1 to cT3) and sustained effects (cT2 to cT3). Sidak Type-I error rate adjustment (which has higher power than Bonferroni) will be applied for the multiple pairwise time point comparisons.¹²² Additionally, longer term sustained effects will be captured for the immediate Tele-Savvy group using the additional follow-up times at T4 and T5 for this group. The proposed study design has the advantage of capturing 3 "baseline" time points for the wait-list attention control and usual care groups which will provide an excellent opportunity to evaluate what if any potential "placebo" effects there may be from being enrolled in this type of study.¹²³ These initial

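### The primary test is an overall three-arm group-by-time test with no prespecified Tele-Savvy versus attention-control contrast, so it can be positive when those two arms are identical

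*Combined protocol and SAP*

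**What the plan says.** Under Power Analysis and Sample Size Determination, detectable effects are given "for the primary intervention test (group-by-time effect) comparing the outcomes of the three group changes" from T1 to T3, described as a "3-by-3 repeated measures design of three groups measured at three time points". The stated result is Cohen's f = 0.21 to 0.24 "may be detected for the main effects for group, time and group-by-time interaction effects", at 80% power and a 5% level, with correlations of 0.3 to 0.5.

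The analysis text for Aims 1, 2 and 3(a) gives its purpose as comparing Tele-Savvy with attention control and usual care. The means it names is that "the first 3 time points will be used to test for differences between the 3 group longitudinal trajectories". The only follow-up comparisons listed are "planned post hoc comparisons for immediate effects (cT1 to cT2), longer term effect (cT1 to cT3) and sustained effects (cT2 to cT3"; these are time points in the data pooled across arms around receipt of Tele-Savvy. The Sidak adjustment "will be applied for the multiple pairwise time point comparisons".

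Three other places bear on the point. Data Collection mentions a direct comparison between groups at 3 and 9 months, without naming arms, a contrast or an alpha. The analysis text promises 95% confidence intervals around means by group and period, not around differences between arms. The attention-control section says that this arm supplies equal attention and is not expected to affect the key mediators.

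**The concern.** Attention control matches Tele-Savvy on the number of modules and on videoconference format and length, and differs in content. Only Tele-Savvy versus attention control separates the program's content from the attention it brings. The overall interaction does not isolate that comparison: it rejects when any arm's trajectory differs from any other, including when attention control differs from usual care and Tele-Savvy adds nothing.

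The plan does not say how a significant overall result leads to a conclusion about Tele-Savvy. The arm pair, the visits and the error control would be chosen after the data are seen, or the overall p-value would stand in for program efficacy. Either way, the trial's main claim would rest on a test that is not specific to it.

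**Working it through.** **Inputs from the plan.** Three arms, three visits, alpha 5%, power 80%, r = 0.3 to 0.5, final N = 215. The printed arm sizes 86/86/54 sum to 226. Taking 20% from 108/108/54 gives 86/86/43, which sums to 215 and is used here.

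**Assumptions not in the plan.** Compound symmetry; effects in SD units; the time profile of the effect; attention control's share of it; the size of a difference confined to usual care.

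**1. The plan's own figure.** Noncentral F with λ = N·f² and N = 215 gives, at 80% power:
- group (2, 212 df): f = 0.213
- time (2, 424 df): f = 0.212
- group-by-time (4, 424 df): f = 0.237

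These round to the stated 0.21 to 0.24. The upper figure is the 4-df interaction, so the sample size does refer to the overall test.

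**2. Rejection when Tele-Savvy equals attention control.** Let usual care alone be worse by d at T2 and T3. With n_U in usual care,

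λ = [n_U(N − n_U)/N] · d² · (2/3)/(1 − r), with 43 × 172/215 = 34.4.

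| d (assumed) | r | λ | Overall test rejects | Tele-Savvy vs attention control rejects |
|---|---|---|---|---|
| 0.2 SD | 0.3 | 1.31 | 12% | 5% |
| 0.2 SD | 0.5 | 1.83 | 16% | 5% |
| 0.4 SD | 0.3 | 5.24 | 41% | 5% |
| 0.4 SD | 0.5 | 7.34 | 56% | 5% |

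If 54 are analysed in usual care (54 × 172/226 = 41.1), the ranges become 14 to 18% and 48 to 65%.

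**3. Detectable difference for the focused contrast.** The change mean(T2, T3) − T1 has variance (1 + r)/2 + 1 − 2r = 1.5(1 − r). With 86 per arm, the detectable difference is 2.80 × √[1.5(1 − r) × 2/86]:
- r = 0.3: 2.80 × √(1.05 × 2/86) = 2.80 × 0.156 = 0.44 SD
- r = 0.5: 2.80 × √(0.75 × 2/86) = 2.80 × 0.132 = 0.37 SD

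**4. Power of that contrast against the overall test.** Each effect is scaled so that the overall test has 80% power (λ = 12.07) when attention control equals usual care. For a sustained effect, 86 × 129/215 = 51.6, so d² = 12.07 × 1.5(1 − r)/51.6. That gives d = 0.50 SD at r = 0.3 and 0.42 SD at r = 0.5. Powers are the same at both correlations.

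| True pattern | Overall test | Averaged Tele-Savvy vs attention control |
|---|---|---|
| Sustained over T2 and T3, controls alike | 80% | about 89% |
| Halved by T3, controls alike | 80% | 78% |
| Growing linearly to T3, controls alike | 80% | 78% |
| At T2 only, controls alike | 80% | 35% |
| Sustained, attention control has half the effect | 54% | 35% |

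For sustained effects, the focused contrast falls below the overall test once attention control has more than about 27% of Tele-Savvy's effect.

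**The case against.** The strongest reply is that the plan intends the right comparison: the analysis sentence states the aim of comparing Tele-Savvy with both controls, and the reported group means would show Tele-Savvy and attention control overlapping if they did. That is fair on intent, and it is conjecture that a positive overall result would be misread. It does not supply a test, a testing order or an alpha.

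A second reply is that the plan expects attention control to be inert, so a pattern confined to usual care is unlikely, and the 0.2 and 0.4 SD values are not the plan's. This stands as a limit on the size: at 0.2 SD the excess over 5% is modest. But the attention arm exists because inertness cannot be taken for granted.

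Third, the 4 df come from the power calculation; the mixed model allows linear trajectories, and linear time would give a 2-df interaction. This removes almost all of the power difference: for a linear effect with controls alike, the 2-df test has 88.3% power against 88.6% for Tele-Savvy versus attention control on the T3 − T1 change. It does not make the overall test specific to Tele-Savvy.

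A reader might also infer that the overall test is always weaker than a direct contrast, or that switching gives up power only against patterns confined to usual care. Neither is supported. The plan does not assume a flat effect; it treats immediate, longer-term and sustained effects as separate questions. The averaged contrast loses power against some real Tele-Savvy effects.

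**Conclusion.** The concern holds on specificity. The named primary test is an overall three-arm test, and nothing prespecified turns it into a statement about Tele-Savvy against attention control. Under compound symmetry with 86/86/43 and r = 0.3 to 0.5, it is positive 12 to 16% of the time (0.2 SD) or 41 to 56% of the time (0.4 SD) when usual care alone differs, against 5% for the focused contrast. Those two differences are illustrative assumptions.

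Power is not a general argument for the change. The advantage of about 9 points depends on the controls behaving alike, a sustained effect and a contrast matched to it; it shrinks or reverses otherwise.

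**What to change.** In the power section and the analysis text for Aims 1, 2 and 3(a):

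- Base the efficacy claim on a prespecified Tele-Savvy versus attention-control contrast in change from T1, from the same three-arm mixed model, two-sided 5%.
- If it is significant, test Tele-Savvy versus usual care at 5% in fixed sequence.
- Report the overall interaction and attention control versus usual care as supportive.
- State in advance whether the contrast is at T2, at T3 or averaged over both, with the expected time course as the reason.
- Restate the detectable difference for the chosen form. For the average of T2 and T3, it is about 0.37 SD (r = 0.5) to 0.44 SD (r = 0.3) with 86 per arm and 80% power.

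Contrasting Tele-Savvy with the two controls pooled is not a substitute: when Tele-Savvy equals attention control and usual care differs by the amount used in step 4, it still rejects 21 to 27% of the time.

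The change needs wording and a restated calculation, with no new participants or data. Its real cost is the power lost if the effect is confined to T2 or attention control is partly active, with a slight loss if the effect fades or grows; the plan should say so. The 5% applies per outcome. The aims list several outcomes, and multiplicity across them needs its own rule.

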We seek to make an effective psychoeducation program widely available to family caregivers of persons living with Alzheimer's disease and related disorders. Taking advantage of the growing use of and familiarity with the internet by persons of caregiving age, the project will advance us toward that goal. We will test the program in an established context of collaboration among the Outreach, Recruitment, and Education Cores of four NIA-supported Alzheimer's Disease Centers (ADC). We will employ a wait-list randomized design in which 18 blocks of 15 caregivers each will be assigned either to immediate Tele-Savvy participation groups or to attention control or usual care groups that are invited to participate in Tele-Savvy six months after baseline data collection (total n=270). We will pursue 3 aims::

Aim 1. Establish the effectiveness of Tele-Savvy in reducing or retarding the affective impact (burden, depression, anxiety) on caregivers associated with dementia family caregiving

Aim 2. Establish the effectiveness of Tele-Savvy in promoting the quality of life of persons with Alzheimer's (agitation; Quality of Life; affect) whose caregivers are trained by Tele-Savvy

Aim 3. (a) Establish the effectiveness of Tele-Savvy in enhancing caregiver mastery and (b) test the mediating effect of mastery and enactment on Aim 1 & 2 outcomes

We also propose, as an Exploratory Aim, to examine the comparability of the program's efficacy across three racial/ethnic groups (African Americans, Caucasians, and Latino/Hispanics).

Significance and Innovation.

The Landscape. Dementing conditions, including the most prevalent of these, Alzheimer's disease, pose a large and growing problem nationally and worldwide. Unless dramatic breakthroughs occur, the current population of 5.3 million persons living with these conditions will swell to at least 14 million by 2050.¹ These persons are distributed across the landscape, in inner cities, in suburban areas, and in rural America; there is even some evidence that the current and future prevalence of Alzheimer's in rural areas is disproportionate to the rural population's share of the overall population.²⁻⁴ Care for these persons is costly. Total estimated cost of care in 2015 will be \$216 Billion; by 2050, it could exceed \$1 Trillion.¹

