Subjects. Participants will be informal caregivers (family/friends) of persons living with Alzheimer’s disease or another dementia. Participants must be providing at least 4 hours per day unpaid assistance, on average, for a person in the early-middle stage of illness (Clinical Dementia Rating of ≥ 1 by home ADC) who is community-dwelling and for whom there is no established plan for institutionalization in the next six months. Caregiver may or may not reside with their care recipient, but care recipients must live in the community and not in an assisted living facility, nursing home, or another institutional setting. The participant must not be involved in another caregiver training study and must not have participated in in-person Savvy Caregiver Program or Tele-Savvy previously. Each participant must have access to a computer or a mobile device with adequate internet connection, microphone, and speakers (to be able to participate in teleconferences) and be able to use email (this was not a serious barrier in the pilot studies). Participants must be able to read, speak and understand English and have no uncorrectable vision or hearing deficits that might impede participation. Questions posed after explaining the project during eligibility determination and the consent process will be used to gauge caregivers’ cognitive ability to take part in the project. Webcams will be mailed to those caregivers who do not have them for the duration of the entire program and caregivers will be asked to mail webcams back after participation in Tele-Savvy.

Power Analysis and Sample Size Determination Several considerations enter into sample size determination: (1) our wish to accommodate as many caregivers as feasible given time/resources; (2) our experience and prior results from SCP trials; (3) sample and effect sizes/attrition rates in recent dementia CG

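### The pooled before-after change that the plan calls the overall intervention effect has no untreated comparator, so its d=0.19 is not a detectable program effect; the randomised primary test is unaffected

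*Combined protocol and SAP*

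**What the plan says.** The plan has two analyses for Aims 1, 2 and 3(a).

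- **Randomised comparison.** The section Power Analysis and Sample Size Determination names the group-by-time comparison of the three arms over T1, T2 and T3 as the primary intervention test. The section Aims 1, 2 and 3 (a) repeats it: the first three time points are used to compare the arms' trajectories.
- **Pooled analysis, introduced as an addition.** The power section describes "the overall intervention effect of the Tele-Savvy program for the combined T1-to-T3 pre-post effects for the immediate Tele-Savvy group", pooled with the six-month change that each wait-list arm shows once it receives Tele-Savvy. It expects 215 people in this pool and presents that number as enough "to perform a pre-post test to detect a small effect size of $d=0.19$ at 80% power and 5% significance level". The analysis section says "we will combine the intervention effects for the three groups across the main 3 time points from just before receipt of the intervention", with time re-aligned as "T1-to-T2-to-T3 for the immediate group and T3-to-T4-to-T5 for the attention control and usual care groups respectively". The re-aligned points are called cT1, cT2 and cT3. Overall time effects are tested, along with Sidak-adjusted pairwise comparisons of time points.

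The only adjustment stated for the pooled model is for differences between arms at cT1, if these are significant. The same section says that T1-T3 data from the wait-list arms will be used to look for placebo-type effects and for decline. It does not say that either result will enter the pooled estimate.

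Aim 1 is to "Establish the effectiveness of Tele-Savvy in reducing or retarding the affective impact (burden, depression, anxiety) on caregivers".

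**The concern.** All three arms contribute only the six-month window that begins just before they receive Tele-Savvy. No untreated window is in the pool, so nothing separates the program from whatever else changes over six months: the course of a progressive illness, regression to the mean, or familiarity with the interview. Aligning the arms at cT1 makes their starting points comparable, but it leaves any trend over time in place.

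The direction of the error depends on the direction of drift. Drift toward improvement is counted as benefit. Drift toward worsening hides benefit, and a program that only slows worsening can show no change or a net decline. Slowing is part of Aim 1, and it can be seen only against an untreated course.

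At stake is how the results are read. The plan attaches the label of overall intervention effect, and a favourable d=0.19, to this uncontrolled quantity. It gives no rule for which result governs if the pooled and randomised analyses disagree.

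**Working it through.** **Inputs.** From the power section: n=215, d=0.19, 80% power, 5% level, 20% attrition, and final arm sizes of 86, 86 and 54. Those arm sizes sum to 226, not 215. The total of 215 fits 43 in usual care (54 × 0.8 = 43.2), so 43 is used below and 54 is shown as an alternative. Two-sided testing is assumed because the plan does not state sidedness. Drift sizes are assumptions.

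**1. Reproduce the plan's figure.** For a one-sample test of mean change, n = ((1.960 + 0.842)/d)². With d=0.19 this is 217.4, so 218; the t test needs 220. At n=215, power for d=0.19 is 79.2%, and the smallest detectable d is 2.802/√215 = 0.191. A one-sided test would need only 172 and does not fit. The figure is therefore that of a single-group, two-sided test of change, and the formula has no comparator term.

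**2. No program effect, drift toward improvement.** The chance of a significant improvement is approximately 1 − Φ(1.971 − δ√215), with √215 = 14.66 and δ the drift in SD of change.

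| Drift toward improvement | False benefit |
|---|---|
| 0 | 2.5% |
| 0.05 | 11% |
| 0.10 | 31% |
| 0.19 | 79% |

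For example, at 0.10: 1.971 − 1.466 = 0.505, and 1 − Φ(0.505) = 0.31. The last row equals the test's power by construction, because the drift is set equal to the detectable effect.

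**3. No program effect, drift toward worsening.** False benefit becomes rarer than nominal: about 0.4% at 0.05 and 0.03% at 0.10. The error in this direction is missed benefit, shown next.

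**4. True benefit of 0.19, natural worsening.** The net change is 0.19 minus the drift.

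| Natural worsening | Net change | Chance of significant improvement |
|---|---|---|
| 0 | 0.19 | 79% |
| 0.05 | 0.14 | 53% |
| 0.10 | 0.09 | 26% |
| 0.19 (worsening fully halted) | 0 | 2.5% |

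**5. What a controlled contrast detects.** For the difference between arms in T1-T3 change, drift common to the arms cancels. The smallest detectable difference at 80% power is 2.802 × √(1/n₁ + 1/n₂).

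| Contrast | Detectable (SD of change) | Power at 0.19 |
|---|---|---|
| Tele-Savvy 86 v attention control 86 | 0.43 | 24% |
| Tele-Savvy 86 v usual care 43 | 0.52 | 17% |
| Tele-Savvy 86 v usual care 54 | 0.49 | 19% |
| Tele-Savvy 86 v both controls 129 | 0.39 | 28% |

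These are simple pairwise contrasts of change, not the plan's three-group mixed model. They put the controlled comparison on the same scale as d=0.19.

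**6. Whether one model for T1-T5 would recover precision.** Generalised least squares was run with arms of 86, 86 and 43, equal correlation of 0.3 to 0.5 between visits (the plan's range), categorical months, Tele-Savvy exposure by time since start, and a Healthy Living term. Compared with T1-T3 alone, the standard error of the six-month effect falls from 0.178 to 0.175 SD at r=0.3 (2%) and from 0.162 to 0.156 at r=0.5 (4%). If Healthy Living is allowed to carry over into months 9 and 12, there is no gain.

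**The case against.** The strongest reply is that the controlled analysis is already the named primary test and the pooled one is only an addition. That stands. A reader might infer that the trial's effectiveness claim rests on an uncontrolled comparison, or that slowing of worsening cannot be shown at all. The documents do not support either reading, because the randomised T1-T3 comparison has concurrent controls and can show slowing.

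It can also be said that the plan foresees drift, since it assigns wait-list T1-T3 data to placebo-type effects and decline. This stands in part: the data and the intention are there, but nothing ties them to the pooled estimate.

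A further tempting reading is that progression of the illness would often produce a false benefit. Step 3 shows the opposite: worsening makes a false benefit rarer. The rates of 11%, 31% and 79% apply only to drift toward improvement.

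Finally, a reader might argue that the delayed arms' window is biased because eligibility requires a care recipient "for whom there is no established plan for institutionalization in the next six months", a screen that lapses as that window opens. The two windows do cover different months, but the documents give neither size nor direction for any resulting difference, so nothing here rests on it.

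**Conclusion.** The concern holds for the pooled cT1-cT2-cT3 analysis and for its power statement, and no further. That analysis estimates program effect plus drift, and its d=0.19 is the detectable size of a mean change in treated people, not of a program effect. The controlled contrasts detect 0.39 to 0.52 SD of change, about two to nearly three times as large. A null randomised result beside a significant pooled change is therefore a realistic outcome, and the plan should say in advance how it would be read.

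The error rates rest on assumed drift of 0.05 to 0.19 SD of change. They show sensitivity and do not predict what will happen. That the pooled estimate has no comparator does not depend on those values. This is a point that should be fixed; it does not undermine the primary test.

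**What to change.** In the sections Power Analysis and Sample Size Determination and Aims 1, 2 and 3 (a):

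1. State that effectiveness conclusions for Aims 1, 2 and 3(a) rest on the randomised T1-T3 between-arm contrast.
2. Relabel the pooled analysis as uncontrolled change over the program period, and report it beside the wait-list arms' T1-T3 change. Usual care is the closer of the two to an untreated course, since attention control receives Healthy Living.
3. Remove d=0.19 as power for an intervention effect.

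An optional addition is one model for T1-T5 in all arms, with categorical months since baseline, time-varying Tele-Savvy exposure and a Healthy Living term. It would remove common drift. However, no arm is untreated at months 9 and 12, the model assumes the same program effect in both windows, and it gains at most about 4% in standard error over T1-T3 alone. It is not needed to resolve the point.

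The cost is a change of wording and one extra reported comparison from data already scheduled. The trial gives up a favourable d=0.19.

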Monthly team videoconferences will be conducted to discuss project progress, recruitment, data collection and analysis, and other issues. The Emory coordinating team will meet weekly. The site co-

investigators and [name] will also meet annually at the ADC Directors' meeting. Additional Data Safety Monitoring Board committee meetings will be held mid-year in years 2 and 3.

Scientific Approach

Design. We aim to enroll 375 subjects in 25 cohorts of 15 subjects each, starting in project month 9 (see project timeline). We expect to enroll, on average, four cohorts per quarter through project year 2 1/2. Recruitment of every 2 cohorts (30 participants total) is scheduled to take place every 6 weeks. We will use a three-arm design with participants randomly assigned on a 2:2:1 ratio to immediate participation in the Tele-Savvy intervention (N=108), immediate participation in an attention control condition (Healthy Living) (N=108), and a usual care condition (N=54). There will be five data-collection points evenly spaced across 12 months. Those in each cohort's intervention condition will take part in Tele-Savvy immediately following baseline data collection. Those in the attention control and usual care conditions will take part in Tele-Savvy after a delay of 6 months (following the 6-month data collection point). Below, we describe the preparation activities in which we will engage (facilitator training and material revisions) and then describe the trial itself. Four NIA-supported Alzheimer's Disease (Research) Centers will collaborate in recruitment, and Emory University will serve as the coordinating center. Emory will be responsible for randomization of subjects (recruits from all sites will be pooled together for randomization), for delivery and fidelity monitoring of the intervention and attention control condition, and for all data gathering and analysis.

Please see the added document for Amendment 8.

Project Timeline, by Quarters

Main Project Activities	Year 1				Year 2				Year 3				Year 4			
	1	2	3	4	1	2	3	4	1	2	3	4	1	2	3	4
Staffing; Training; Finalizing																
DSMB scheduled meetings		X			X				X				X			X
Enroll 18 cohorts (15 each) + Acquisition	30	60	90	120	150	180	210	240	270							
Data Collection																
Data Cleaning and Analysis																
Dissemination																

Preparation.

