data captured at T1-T2-T3 for the delay group will also be used to evaluate any potential decline occurring during this time period. All model assumptions will be tested; grand mean centering used to help combat multicollinearity between variables; and standard diagnostic tests and influence statistics used to test the distributions of the residuals. MLM models utilize all available data for all participants at each time point and have the advantage of adjusting for the missing data over time, where repeated measures ANOVAs do not. Further covariate predictors of missingness over time will be included to additionally adjust for these confounders¹²⁴ To aid in final interpretation we will include the 95% confidence intervals around means by intervention group and time period. SPSS v.22 will be used for all analyses at the 5% significance level.¹²²

Aim 3(b). To test the mediating effect of mastery on Aim 1 & 2 outcomes, we will employ the PROCESS add-on module for SPSS¹²⁵ which includes performing the combined approaches of Baron and Kenney, the Sobel test, as well as semi-parametric estimation and testing of the Sobel test through bootstrapping. The focus will be on both the immediate (T2 for immediate Tele-Savvy group and T4 for attention control and usual care groups pooled together) and sustained (T3 for immediate Tele-Savvy group and T5 for attention control and usual care groups pooled together) effects of Tele-Savvy on the mediating measure of mastery on the Aim 1 and Aim 2 outcomes of caregiver burden, depression, anxiety, and dyadic relationship and PLWD BPSD, agitation, mood, and quality of life. These indirect/mediation effects will also be tested and evaluated using structural equation modeling via AMOS v.22.¹²⁶

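### The pooled pre-post power figure (d=0.19, 80%) uses an unadjusted 5% level, but the analysis tests that contrast as one of three Sidak-adjusted pairs; with 215 analysed the detectable effect is 0.22

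*Combined protocol and SAP*

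**What the plan says.** All places are in the combined protocol and SAP.

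- **Power Analysis and Sample Size Determination.** The overall Tele-Savvy effect is to be estimated by pooling "the combined T1-to-T3 pre-post effects for the immediate Tele-Savvy group plus the T3-to-T5 pre-post effects from the AC and UC groups". The pooled sample is put at 215, for a "pre-post test to detect a small effect size of $d=0.19$ at 80% power and 5% significance level". The paragraph does not mention a multiplicity adjustment. The 215 rests on this enrolment: "we will enroll 270 CGs (108 for TS and AC groups and 54 for UC group"), less 20% attrition.
- **Aims 1, 2 and 3 (a).** The pooled time points are relabelled cT1, cT2 and cT3. An overall time effect is assessed, together with "planned post hoc comparisons for immediate effects (cT1 to cT2), longer term effect (cT1 to cT3) and sustained effects (cT2 to cT3"). The text then states: "Sidak Type-I error rate adjustment (which has higher power than Bonferroni) will be applied for the multiple pairwise time point comparisons".
- **End of the same analysis text.** "SPSS v.22 will be used for all analyses at the 5% significance level".
- **Design.** The enrolment target differs from the one in the power section: "We aim to enroll 375 subjects in 25 cohorts of 15 subjects each". The arm sizes printed in the same paragraph (108, 108 and 54) still add to 270.

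**The concern.** The powered contrast runs from just before Tele-Savvy to the second assessment after it: T1 to T3 in the immediate arm and T3 to T5 in the two delayed arms. In the analysis section this is cT1 to cT3, one of the three adjusted pairs. The power section therefore quotes a significance level that the analysis will not use for that contrast.

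A reader who takes the power paragraph at face value will believe that an effect of 0.19 would be missed about one time in five. Under the stated testing rule and 215 analysed, it would be missed about one time in three. A non-significant adjusted result could then be read as stronger evidence against a small effect than it is.

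**Working it through.** **Inputs**

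- Analysed n = 215, d = 0.19, power 80%, level 5% (power section). Sidedness is not stated.
- Three pairwise comparisons with Sidak adjustment (Aims 1, 2 and 3 (a)).
- Enrolment of 270 (power section) or 375 (Design). Attrition of 20% (power section) or 25% (Limitations and Challenges).

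**Method.** Paired t-test with n−1 degrees of freedom and noncentrality d√n, where d is the mean change divided by the SD of change.

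**Step 1: reproduce the plan's figure.** The noncentrality is 0.19 × √215 = 2.786. The two-sided 5% critical value on 214 df is 1.971. Power is 79.2%, and d for 80% power is 0.192. The normal approximation agrees: (1.960 + 0.842)/√215 = 0.191. A one-sided 5% test would give 87.1% power and d=0.170, so it does not reproduce. The stated figure is one unadjusted two-sided test.

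**Step 2: the level used in the analysis.** For three comparisons, Sidak gives 1 − 0.95^(1/3) = 0.01695. The documents do not print this level; it follows from the method they name.

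**Step 3: recompute at that level, n = 215.** The critical value on 214 df is 2.407. Power at d=0.19 is 64.8%, and d for 80% power is 0.222. The normal approximation gives (2.388 + 0.842)/√215 = 0.220. Reaching 80% power at d=0.19 would take 292 analysed.

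**Step 4: sensitivity to the analysed n**

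| Analysed n | Source | Power at d=0.19, Sidak | Detectable d, Sidak |
|---|---|---|---|
| 202 | 270 × 0.75 | 61.5% | 0.229 |
| 215 | as stated (270 × 0.80 = 216) | 64.8% | 0.222 |
| 226 | printed arms, 86+86+54 | 67.4% | 0.216 |
| 281 | 375 × 0.75 | 78.3% | 0.194 |
| 300 | 375 × 0.80 | 81.3% | 0.187 |

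The printed arms do not add to 215; that total would need 43 in usual care (86+86+43).

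**Step 5: could the figure refer to the overall time test?** That test has 2 numerator df and is not Sidak-adjusted. Under compound symmetry, with 0.19 between cT1 and cT3, its noncentrality is 215 × 0.19² = 7.76 if cT2 lies midway, and 4/3 of that, 10.35, if cT2 equals cT3. Power at 5% on 2 and 428 df is 70% and 83% respectively.

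**Step 6: the gated alternative.** The rule is the overall time test at 5% and, only if it is significant, each pair at 5%. With three means this holds familywise error. If all three are equal, the overall test protects; otherwise at most one pair is truly null, and it is tested at 5%. Simulated at n = 215 with correlations of 0.3 and 0.5 (multivariate overall test, then paired t), power for cT1 to cT3 at d=0.19 is about 68% with half the effect present at cT2, 70% with three quarters, and 74 to 75% with all of it. Sidak gives about 65% in each case.

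**The case against.** Four points can be made for the plan.

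1. **This is not the primary test.** The power section gives that name to the three-group, three-time-point comparison and powers it separately (f = 0.21 to 0.24). The pooled contrast is an additional analysis, and 270 was chosen partly to accommodate as many caregivers as feasible. This stands. A reader might infer that the trial as a whole is underpowered; the documents do not support that. They also do not present 0.19 as an expected or minimum important effect. The pilot's significant pre-post effects were 0.40 to 0.55, and with 215 analysed the Sidak-adjusted test has 97.6% power at d=0.30.

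2. **Enrolment may now be 375.** If so, 281 to 300 would be analysed and the shortfall all but disappears. This stands as a limit on size. The mismatch in level remains at any n, and the power section still works from 270 and 215.

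3. **The sentence may mean the unadjusted overall time test,** since it speaks of an overall effect. This is weaker. The text describes a pre-post test between two named time points, and 0.19 reproduces as a single paired contrast. Step 5 shows that the overall test would give 70 to 83% power depending on a cT2 mean that the plan does not state.

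4. **Sidak is valid and prespecified.** This stands in full. A reader might infer that the adjustment is itself a mistake, or that gating recovers a fixed 75% power. Neither follows. Gating gains roughly 3 to 10 percentage points over Sidak in the patterns run, depending on the cT2 mean, and it gives up simultaneous confidence intervals.

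**Conclusion.** The point holds as an inconsistency between the power statement and the testing rule. The plan's arithmetic is sound for the test it assumes, but that is not the test the analysis section specifies. With 215 analysed, the pooled cT1-to-cT3 contrast under Sidak detects d=0.22, not 0.19, at 80% power, and has about 65% power at 0.19.

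The 65% should not be read as a settled property of the trial: across the sample sizes that the protocol supports, the range is about 62 to 81%. The result assumes a two-sided test, three comparisons in the Sidak family, and a paired t-test as a stand-in for the mixed-model contrast, which is also the basis on which the plan's own figure reproduces. The consequence is modest: a supporting analysis is described somewhat too favourably, and the primary group-by-time test is unaffected.

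**What to change.** **Needed.** In the power section, state the level used for the pooled contrast and the figure that goes with it. For example: with 215 analysed, and each of the three pairwise time comparisons tested two-sided at the Sidak level of about 1.7%, the detectable pre-post effect is d=0.22 at 80% power. First reconcile the enrolment figures (270 and 375), the attrition rates (20% and 25%) and the arm sizes that add to 226, then recalculate for the resulting n.

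**Optional.** Keep the overall time test that is already planned, and test the three pairs at an unadjusted 5% only if it is significant. If this is chosen, state the assumed cT2 mean beside the power; at d=0.19 with 215 analysed, expect about 67 to 76% depending on that mean.

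**Cost.** Restating the figure takes a sentence or two and gives a slightly less favourable number, with no added participants, visits or data. The optional rule also costs the simultaneous confidence intervals.
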